7.1.2 Stroke Related Expected Adverse Events

In addition to the above, the following AE's have been deemed as potentially relevant to the study. They will therefore be recorded if they occur during the study, and will be monitored throughout the study as deemed appropriate by the PI/CI:

- Death
- Falls
- Further vascular events
- Cardiac events
- Epileptic seizures
- Infections
- Pain
- Mood disturbance
- Deep Vein Thrombosis

If any of these adverse events occur then they will be recorded in the CRF and followed up until either resolution (if appropriate); the end of the study period for that participant, or until the PI deems the AE as stable, whichever is sooner.

All adverse events listed in section 7.1.2 will be recorded from the date of consent, to the end of the trial intervention period (i.e. discharge from hospital).

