4.8 Control

Standard care, as per usual working practice for the stroke unit. Control stroke units will have minimal contact with the research team, other than for data collection. They will be aware of the broad aims of the study, but not the specific detail of the intervention.

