4.10 Training for Intervention Sites

For sites randomised to the intervention arm, all physiotherapists, occupational therapists and therapy assistants will be trained in the ILA. Training is anticipated to last no more than 3 hours. Additional training sessions will be offered if new members join the team during the recruitment phase. A manual including written, photographic and video resources will demonstrate how to adapt standard care interventions to the ILA. Therapists will be able to refer to the manual throughout their involvement in the study.

Whilst the wider multidisciplinary team (e.g. nurses, doctors, other AHP's) will not specifically be asked to change their approach with patients, those at intervention sites will be invited to attend a short education session to raise their awareness of the trial, and will be provided with written information about the study, and the concepts under investigation. As these professions wouldn't typically be analysing movement or giving specific instructions/feedback, this level of engagement is deemed appropriate and realistic.

The therapy team will be encouraged to give the MDT (particularly nurses) specific guidance about how to instruct an individual patient during movement (as part of a manual handling care plan, and in line with the ILA approach). These awareness raising sessions will support the MDT to understand and follow through these instructions.

As part of the training, clinical staff will be reminded of the options to withdraw participants from the study, should there be concerns about the impact the ILA has on their recovery (see 7.1.1).

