7.1 Assessment of Safety

7.1.1 Expected ILA Adverse Events

Although unlikely, there is a possibility that the ILA is perceived as less personal/motivating for patients, and this may be associated with a reduced willingness to participate in therapy. We will monitor adherence with rehabilitation across all sites. Non-compliance will be considered an AE if (i) a patient is declining to participate in rehabilitation sessions over a period of 5 days and (ii) the clinical team are unable to account for this in any other way. This will be addressed on an individual basis through discussion with the patient and the clinical team. If indicated, they will be withdrawn from the study.

If the treating team have any concerns about using the ILA with an individual patient, for example, should they feel that a patient is not responding /recovering as expected, they should discuss this with the Chief Investigator. If indicated, the participant will be withdrawn from the study, and their rehabilitation will revert to standard care. This decision will be taken on an individual basis, following discussion with the clinical team, Chief Investigator and (if appropriate) the participant. Withdrawal due to unanticipated/unexplained lack of progress in rehabilitation will be considered an AE.

It is important to note that, whilst therapists at the intervention sites are encouraged to adhere as much as possible to the ILA guidance, this is a pragmatic trial, and they can use their own clinical judgement during each individual treatment session. This is monitored as part of the feasibility aspect of this trial.

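### Adverse events must be recorded, but no common way of eliciting them is set, so descriptive counts by arm may differ through site ascertainment

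*Combined protocol and SAP*

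**What the plan says.** Section 7.1.2 lists nine events, among them falls, pain and mood disturbance. It requires each to be recorded whenever it occurs, and says that they "will be monitored throughout the study as deemed appropriate by the PI/CI". It then adds "If any of these adverse events occur then they will be recorded in the CRF" and gives the window: "All adverse events listed in section 7.1.2 will be recorded from the date of consent, to the end of the trial intervention period", meaning hospital discharge. None of this differs by arm. The section gives no definition or severity threshold, no standard question, no visit at which the events are asked about, and no named recorder.

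Section 4.12 schedules assessments at baseline, weeks 2, 4 and 6, discharge and 3 months. No AE check is listed at any of them, and no pain or mood item is named at baseline. The research practitioner at each site is not blind. Blinded video scoring covers the outcome measures, and nothing similar is described for AEs.

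Three passages treat the arms differently:
- Section 4.10, on training at intervention sites: "clinical staff will be reminded of the options to withdraw participants from the study, should there be concerns about the impact the ILA has" on recovery.
- Section 7.1.1 gives a route to the Chief Investigator that opens with "If the treating team have any concerns about using the ILA with an individual patient". It ends with "Withdrawal due to unanticipated/unexplained lack of progress in rehabilitation will be considered an AE".
- Section 4.8: "Control stroke units will have minimal contact with the research team, other than for data collection".

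Section 4.16 describes a mainly descriptive analysis and does not mention AEs.

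**The concern.** Where events are not sought in the same way everywhere, the count depends on how actively each site looks and what it regards as worth noting. Pain and mood disturbance are the most exposed of the nine, because the protocol says neither what counts nor how a problem already present at enrolment is told apart from a new one. Sections 4.5.3 and 4.5.3.1 also admit people who lack capacity or have a language impairment, and they may not volunteer such problems.

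The cluster design makes this harder to dismiss as noise. A unit's reporting habit falls wholly into one arm, and analysis cannot recover events that were never written down. Section 4.1 includes testing the integrity of the protocol and informing a Phase III trial among its aims. AE capture is part of what is being piloted, and a weak method carried forward would keep its bias in a larger trial with less sampling noise to hide it.

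**Working it through.** The documents state no AE rate or capture rate, so there is no planned figure to reproduce. The check has two parts.

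**1. What the text makes symmetric and what it does not**
- Same in both arms: the duty to record, the CRF, the consent-to-discharge window (7.1.2), the assessment schedule (4.12), and monitoring of adherence at all sites (7.1.1).
- Left open in both arms: intensity of monitoring, definitions, elicitation and recorder (7.1.2).
- Intervention sites only: the reminder about concerns and withdrawal (4.10) and the route to the Chief Investigator for concerns about the ILA (7.1.1).
- One asymmetry needs no assumption about behaviour. The AE of withdrawal for unexplained lack of progress sits in a paragraph where the patient then goes back to standard care. As written, it has no control-arm counterpart.

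**2. How much unequal capture could matter (illustration)**

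Inputs: 60 participants in 6 to 8 units (4.13). The allocation ratio is not stated, so n = 30 per arm is assumed. The true event rate p is assumed equal in both arms at 20%, 30% or 50%. Capture c is assumed at 90% in the ILA arm and 70% or 50% in control.

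Expected recorded events per arm = n × p × c. For example, 30 × 0.30 × 0.90 = 8.1 and 30 × 0.30 × 0.50 = 4.5. The ratio is c(ILA) / c(control) and does not depend on p: 0.90/0.70 = 1.29 and 0.90/0.50 = 1.80.

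With a = p × c(ILA) and b = p × c(control), the 95% half-width for the risk difference is 1.96 × √[a(1−a)/30 + b(1−b)/30]. For a = 0.27 and b = 0.15 this is 1.96 × √(0.3246/30) = 0.204.

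| True rate | Capture ILA / control | Recorded ILA v control | Difference | Ratio | 95% half-width |
|---|---|---|---|---|---|
| 20% | 90% / 70% | 5.4 v 4.2 | 4 points | 1.29 | 18.5 points |
| 20% | 90% / 50% | 5.4 v 3.0 | 8 points | 1.80 | 17.4 points |
| 30% | 90% / 70% | 8.1 v 6.3 | 6 points | 1.29 | 21.6 points |
| 30% | 90% / 50% | 8.1 v 4.5 | 12 points | 1.80 | 20.4 points |
| 50% | 90% / 70% | 13.5 v 10.5 | 10 points | 1.29 | 24.7 points |
| 50% | 90% / 50% | 13.5 v 7.5 | 20 points | 1.80 | 23.6 points |

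Equal capture gives 1.00. If control units looked harder, the ratios would invert to 0.70/0.90 = 0.78 and 0.50/0.90 = 0.56. In every row the spurious difference is smaller than its half-width, before any allowance for clustering.

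**Weight of one unit.** With equal numbers of units per arm, each arm has 3 or 4, so one unit supplies about a third or a quarter of its arm. Section 5.2 describes four discussion groups, one per intervention site. If only six units joined, control would have two, each supplying about half of that arm.

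**The case against.** A reader might infer that AE recording itself is discretionary. It is not: recording is required, and the discretion attaches only to monitoring.

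A reader might also infer that control units are cut off from AE collection. Section 4.8 exempts data collection from its minimal contact, and entering AEs in the CRF is naturally read as data collection.

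A third inference is that ILA staff are primed to report pain or low mood. The reminder in section 4.10 and the route in section 7.1.1 concern withdrawal and recovery under the ILA. Neither asks anyone to look for the events in section 7.1.2, so a link to pain or mood would be conjecture.

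The CRF is not among the documents and may contain a prompt. Recording only events that occur after consent could be read as excluding existing problems. Knowledge of allocation is stated for the research practitioner, while no AE recorder is named. Finally, no between-arm AE comparison is planned, a steering committee that includes a statistician oversees the trial (7.2), and the illustrated differences lie within sampling error.

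These points stand and limit the claim. They leave intact the absence from the protocol of common elicitation, of definitions for pain and mood disturbance, and of a baseline record of either, in a design where site habits and arm coincide.

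**Conclusion.** The point holds as a gap in ascertainment. Descriptive AE counts by arm may differ because of how units look for events, and the protocol contains nothing to prevent or detect this. Neither the direction nor the size is known. The ratios of 1.29 and 1.80 rest on assumed capture rates, equal true rates and an equal split of 60 participants, and equal capture gives 1.00.

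The documents do not support the stronger conclusion that the ILA arm will over-report, or that the pilot will reach a wrong inference about safety: no such inference is planned. The consequence is limited to the reliability of the descriptive safety counts and what Phase III planning takes from them. That is enough to justify a change, because the remedy is cheap and missing records cannot be recovered at analysis.

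**What to change.** 1. In section 7.1.2, replace the discretionary monitoring wording with one checklist of the nine events: yes/no, onset date, and new or worse since enrolment. Add a short working definition of pain and of mood disturbance.
2. Have the research practitioner complete it in both arms at baseline and at the visits already in section 4.12 up to discharge (weeks 2, 4 and 6 where the patient is still in hospital, and discharge). Continue to log spontaneous reports between visits.
3. State whether the withdrawal AE in section 7.1.1 has a control-arm counterpart. If not, report it separately from the other AEs.
4. In section 4.16, say that AE counts by arm are descriptive and rest on unblinded ascertainment. The checklist makes the questioning alike across arms but does not blind whoever completes it.

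The cost is a CRF page, a few minutes per visit by staff already present, and more minor events recorded. No additional visit is needed.

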7.1.3 Serious Adverse Event Reporting

For this study (and in accordance with HRA guidance), a serious adverse event (SAE) is defined as an untoward occurrence that:

- (a) results in death
- (b) is life-threatening
- (c) requires hospitalisation or prolongation of existing hospitalisation
- (d) results in persistent or significant disability or incapacity
- (e) consists of a congenital anomaly or birth defect;
- (f) is otherwise considered medically significant by the investigator.

Serious Adverse Events will be recorded in the medical notes and in the CRF. If the event is deemed to be related to the intervention, the SAE will be submitted to the Sponsor immediately. The Sponsor or CI will inform the Research Ethics Committee within 15 days of the CI becoming aware of the event. The acknowledgement of the receipt of the SAE will be sent to the RBCH R&D directorate. SAEs which are not related to the intervention will be recorded as other AEs.

For this study there are no expected adverse events.

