4.12 Measures

Measures will be performed and recorded by the stroke research practitioner(s), or designated clinician, at each site. As the research practitioner will not be blind to the intervention arm, all measures will be video recorded, and later scored by a blinded second assessor. Frequent measures are required to understand *rate* of change. Outcome measures have been selected with consideration of international recommendations for measurement of sensorimotor recovery in stroke [12].

At baseline:

- Movement Specific Reinvestment Scale (Self-Report Questionnaire) (MSRS)

At baseline, week 2, week 4, week 6 post enrolment (or up to the point of discharge):

- Fugl Meyer – motor leg sub section
- Modified Postural Adjustment in Stroke Scale (SwePASS)
- Modified Rivermead Mobility Index (mRMI)
- Able to sit for 1 minute unsupported?
- Able to transfer from bed to chair independently?
- Able to walk 10m independently?

At point of discharge

- Discharge destination and care requirements immediately on discharge (number of care visits per day multiplied by the number of carers required)
- Fugl Meyer – motor leg sub section
- Modified Postural Adjustment in Stroke Scale (SwePASS)
- Modified Rivermead Mobility Index (mRMI)
- Able to sit for 1 minute unsupported?
- Able to transfer from bed to chair independently?
- Able to walk 10m independently?
- Movement Specific Reinvestment Scale (MSRS)

At 3 months post enrolment:

- Fugl Meyer – motor leg sub section
- Modified Postural Adjustment in Stroke Scale (SwePASS)
- Modified Rivermead Mobility Index (mRMI)
- Able to sit for 1 minute unsupported?
- Able to transfer from bed to chair independently?
- Able to walk 10m independently?
- Modified Rankin Scale (mRS)
- EQ-5D
- Movement Specific Reinvestment Scale (MSRS)

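### Section 7.1.3 defines an SAE by seriousness alone, then re-files unrelated SAEs as other AEs, so the serious label depends on a relatedness judgement with no named or blinded assessor

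*Combined protocol and SAP*

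**What the plan says.** Section 7.1.3 opens with a definition: "a serious adverse event (SAE) is defined as an untoward occurrence that" meets any of criteria (a) to (f), which run from death to medical significance. None of the six mentions cause. Three rules follow:

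- Recording: "Serious Adverse Events will be recorded in the medical notes and in the CRF".
- Expedited reporting: "If the event is deemed to be related to the intervention, the SAE will be submitted to the Sponsor immediately".
- Filing of the rest: "SAEs which are not related to the intervention will be recorded as other AEs".

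The section closes with "For this study there are no expected adverse events". Yet the headings of 7.1.1 and 7.1.2 both announce expected adverse events, and 7.1.2 introduces its list by saying that "the following AE's have been deemed as potentially relevant to the study". That list has nine entries, including death, further vascular events, infections and deep vein thrombosis. Its entries are recorded from consent until hospital discharge.

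On blinding, section 4.12 says that "the research practitioner will not be blind to the intervention arm". The blinded assessors described in sections 4.11 and 4.12 score videos of the outcome measures. Under section 4.8 the control is the stroke unit's usual practice. Section 4.16 covers recruitment, retention, fidelity and outcome scores, and specifies no summary of AEs or SAEs. Section 7.2 sets up the TSC without saying what safety data it receives.

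**The concern.** Seriousness describes what happened to the participant; relatedness is an opinion about why. Safety recording normally keeps them apart, so that serious events can be counted in each arm before anyone attributes them. The filing rule makes the first depend on the second. Any later count of SAEs would then be a count of attributed events, and attribution is not equally available in the two arms.

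This matters even in a pilot. One aim is to test the integrity of the protocol and another is to inform a Phase III trial, which could inherit the rule. Section 4.5.3 also justifies enrolling people who lack capacity partly on the ground that the intervention carries negligible risk. A complete list of serious events by arm is the direct check on that statement.

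**Working it through.** The plan gives no safety figure to reproduce, so the check is mainly a reading of the rules side by side.

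**1. Definition against filing rule (7.1.3).** Take a death judged unrelated. It meets criterion (a), so it is an SAE by definition. Under the filing rule it is recorded as an other AE. The two statements give the same event different labels.

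**2. Is the filing rule only about the reporting route?** Limiting immediate submission to related SAEs is already done by the preceding reporting sentence. If the filing sentence meant only that, it would add nothing. Read literally, it changes how the event is recorded.

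**3. Who judges relatedness?** Section 7.1.3 uses a passive construction and names nobody. The research practitioner is unblinded, therapists at intervention sites have been trained in the ILA (4.10), and blinded review is described only for outcome videos. That unblinded staff would judge relatedness is a likely inference. It is not a stated rule.

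**4. Symmetry between arms.** A control participant receives usual practice (4.8). There is no trial intervention to which the event could be related, so a labelled SAE is unlikely in that arm whatever the true rate.

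**5. Where a re-filed event lands.** The list and the discharge cut-off in 7.1.2 apply to the listed AEs. Section 7.1.3 sets neither a list nor a window for SAEs. Assessments continue to 3 months after enrolment (4.12). A serious event off the list, or a readmission after discharge (criterion (c)), therefore has no clear recording rule once it is treated as an other AE. Section 7.1.2 also speaks of events during the study, which fits poorly with stopping at discharge.

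**6. Illustration of the mechanism.** The only input from the plan is the total of 60 participants (4.13). Everything else is assumed: 30 per arm; the same true proportion r with a serious event in each arm, one event per person; a share s of ILA-arm events judged related; none in the control arm; independence, with clustering ignored.

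- Serious events per arm = 30 × r
- Labelled SAEs expected in the ILA arm = 30 × r × s; in the control arm = 0
- Chance of no labelled SAE in the ILA arm = (1 − r × s)^30
- Share of all serious events re-filed = 1 − s/2

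| r | Serious events per arm | Labelled in ILA arm, s = 5% to 20% | Chance of none labelled, s = 5% to 20% |
|---|---|---|---|
| 10% | 3 | 0.15 to 0.6 | 0.860 to 0.545 |
| 20% | 6 | 0.3 to 1.2 | 0.740 to 0.294 |
| 30% | 9 | 0.45 to 1.8 | 0.635 to 0.156 |

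The share re-filed runs from 1 − 0.05/2 = 97.5% down to 1 − 0.20/2 = 90%. If control events could also be called related, with s = 10% in both arms, the asymmetry goes but 1 − 0.10 = 90% are still re-filed. These figures show how the rule works. They largely restate the assumed s and are not estimates for this trial.

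**7. Expectedness.** The closing sentence of 7.1.3 denies any expected adverse events; 7.1.1 and 7.1.2 are headed as expected events and describe them. These passages must be reconciled.

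**The case against.** The strongest reply is that no event is lost. Section 7.1.3 sends all SAEs to the notes and CRF without a causal condition, and the listed events, death included, are recorded to discharge whatever their cause. The modified Rankin Scale at 3 months scores death as 6, so later deaths can surface among participants still followed. The CRF is not in the documents and may hold a seriousness flag. This largely stands. A reader might infer that serious events disappear from the safety comparison; the documents do not support that. For listed inpatient events only the label is in doubt, and incomplete capture is a possibility confined to off-list or post-discharge events.

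A reader might also infer that the TSC will see a biased SAE table. No such table is planned, so there is no defined comparison to distort. What remains is that no complete summary is specified.

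A third tempting reading is that staff who know the allocation decide which events count. The plan does not say who decides. The supportable point is that nobody is named and nothing provides for a blinded judgement.

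Finally, the protocol uses the word intervention loosely: the intervention overview in Table 1 has a control column, and 7.1.1 monitors adherence at all sites. So an empty control column is likely rather than certain. That softens step 4 but leaves the conflict between definition and filing rule untouched.

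**Conclusion.** The point holds as a defect in a stated rule. Section 7.1.3 makes the serious label conditional on relatedness, against its own definition, with no named or blinded assessor and with little scope for a usual-care event to qualify. A valid SAE count by arm could not be relied on from that label. Capture of off-list or post-discharge serious events is uncertain because the SAE window is unstated.

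The size cannot be given from the documents; the 90% to 97.5% above rests wholly on assumed shares. The conclusion assumes that sites follow the filing sentence literally and that the CRF has no separate seriousness field. If it has one, the harm is mainly unclear wording. The point should be corrected, but it does not threaten the pilot's feasibility aims.

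**What to change.** Replace the filing sentence in 7.1.3 with: *All events meeting (a)-(f) are recorded as SAEs, with relatedness as a separate field; only related SAEs need expedited reporting.* Then:

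- State the SAE recording window. Serious events can be asked about at the existing 3-month assessment.
- Name the role that judges relatedness.
- List all SAEs by arm, regardless of relatedness, for the TSC and the final report, and say so in 4.16 and 7.2.
- Reconcile the closing sentence of 7.1.3 with the headings and content of 7.1.1 and 7.1.2.

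The cost is protocol wording, separate CRF fields for seriousness and relatedness if they do not already exist, one listing, and a modest amount of post-discharge collection at a visit already planned. The criterion for expedited reporting does not change.
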